6.2. Exclusion Criteria

Participants are excluded from the study if any of the following criteria apply:

Medical Conditions

1. Asthma or a history of asthma (except in childhood, which has now remitted)
2. Significant history of or current cardiovascular, respiratory, hepatic, renal, gastrointestinal, endocrine, hematological, or neurological disorders capable of significantly altering the absorption, metabolism, or elimination of drugs; constituting a risk when taking the study treatment; or interfering with the interpretation of data
3. Abnormal blood pressure [as determined by the investigator]
4. Alanine transaminase (ALT) >1.5x upper limit of normal (ULN)
5. Bilirubin >1.5xULN (isolated bilirubin >1.5xULN is acceptable if bilirubin is fractionated and direct bilirubin <35%).
6. Current or chronic history of liver disease, or known hepatic or biliary abnormalities (with the exception of Gilbert's syndrome or asymptomatic gallstones)
7. Corrected QT interval (QTc) >450 msec

NOTES:

- The QTc is the QT interval corrected for heart rate according to Bazett's formula (QTcB), Fridericia's formula (QTcF), and/or another method, machine-read or manually over-read.
- The specific formula that will be used to determine eligibility and discontinuation for an individual participant should be determined prior to initiation of the study. In other words, several different formulae cannot be used to calculate the QTc for an individual participant and then the lowest QTc value used to include or discontinue the participant from the trial.
- For purposes of data analysis, QTcB, QTcF, another QT correction formula, or a composite of available values of QTc will be used as specified in the Reporting and Analysis Plan (RAP).

Prior/Concomitant Therapy

8. Past or intended use of over-the-counter or prescription medication including herbal medications within 7 days prior to dosing. Specific medications listed in Section 7.7 may be allowed.
9. Live vaccine(s) within 1 month prior to screening, or plans to receive such vaccines during the study

Prior/Concurrent Clinical Study Experience

10. Participation in the study would result in loss of blood or blood products in excess of 500 mL within 56 days
11. Exposure to more than 4 new chemical entities within 12 months prior to the first dosing day

Consider adding the following criteria if participants can only be enrolled once per study.

12. Current enrollment or past participation within the last 90 days before signing of consent in any other clinical study involving an investigational study treatment or any other type of medical research

Diagnostic assessments

13. Presence of Hepatitis B surface antigen (HBsAg) at screening Positive Hepatitis C antibody test result at screening.

NOTE: Participants with positive Hepatitis C antibody due to prior resolved disease can be enrolled, only if a confirmatory negative Hepatitis C Ribonucleic Acid (RNA) test is obtained

14. Positive Hepatitis C RNA test result at screening or within 3 months prior to first dose of study treatment

NOTE: Test is optional and participants with negative Hepatitis C antibody test are not required to also undergo Hepatitis C RNA testing

15. Positive pre-study drug/alcohol screen

16. Positive human immunodeficiency virus (HIV) antibody test
17. Regular use of known drugs of abuse

Other Exclusions

18. Regular alcohol consumption within 3 months prior to the study defined as:
An average weekly intake of >14 units for males and females. One unit is equivalent to 8 g of alcohol: a half-pint (~240 mL) of beer, 1 glass (125 mL) of wine or 1 (25 mL) measure of spirits.
19. Current smoker or a history of smoking within 6 months of Screening, or a total pack year history of >5 pack years.
[number of pack years = (number of cigarettes per day/20) x number of years smoked]
20. Sensitivity to any of the study treatments, or components thereof (including lactose and MgSt), or drug or other allergy that, in the opinion of the investigator or medical monitor, contraindicates participation in the study

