5.4. Scientific Rationale for Study Design

This is the first study that GSK2269557 will be administered via the ELLIPTA DPI formulated in a blend containing 0.4% MgSt. Magnesium stearate has been reduced in this final formulation from that studied in previous trials and has resulted in a change in the respirable mass of the drug product. It is anticipated that this will impact the PK profile in man and resulting in an increase in systemic exposure. Cmax may increase, by an average of approximately 50%-70% compared to the previously studied MgSt containing formulation. The final sampling timepoint (120 hours post-dose) has been

selected to confirm the terminal half-life based on preliminary data from study 205759 in healthy Japanese participants which has shown a half-life of approximately 46 hours.

This study will inform on the exposure of GSK2269557 administered via the ELLIPTA DPI formulated in the new blend containing 0.4% MgSt. Previous studies conducted across healthy participants and patients have shown no major differences in exposure.

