6.1. Inclusion Criteria

Participants are eligible to be included in the study only if all of the following criteria apply:

Age

1. Participant must be 18 to 75 years of age inclusive, at the time of signing the informed consent.

Type of Participant

2. Participants who are overtly healthy as determined by medical evaluation including medical history, physical examination, laboratory tests, and ECG tests. Re-screening will be allowed once, at the discretion of the Principal Investigator in consultation with GSK medical monitor (see Section 6.4).
3. Normal spirometry at Screening forced expiratory volume in 1 second (FEV1) and forced vital capacity (FVC) $\geq 80\%$ of predicted – measurements to be taken in triplicate and the highest value for each component must be $\geq 80\%$ of predicted).

Weight

4. Body weight ≥ 50 kg and body mass index (BMI) within the range 18.0 – 35.0 kg/m² (inclusive).

Sex

5. Male or female

a. Male participants:

A male participant must agree to use contraception as detailed in [Appendix 2](#) of this protocol during the treatment period for at least 5 half-lives + 90 days after the last dose of study treatment and refrain from donating sperm during this period.

b. Female participants:

A female participant is eligible to participate if she is not pregnant (see [Appendix 2](#)), not breastfeeding, and at least one of the following conditions applies:

(i) Not a woman of childbearing potential (WOCBP) as defined in [Appendix 2](#)

OR

(ii) A WOCBP who agrees to follow the contraceptive guidance in [Appendix 2](#) during the treatment period for at least 5 half-lives + 90 days after the last dose of study treatment .

Informed Consent

6. Capable of giving signed informed consent as described in [Appendix 3](#) which includes compliance with the requirements and restrictions listed in the informed consent form (ICF) and in this protocol.

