6.3. Lifestyle Restrictions

6.3.1. Meals and Dietary Restrictions

- Refrain from consumption of Seville oranges, grapefruit or grapefruit juice from 7 days before the start of study treatment until collection of the final pharmacokinetic (PK) sample.

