7.7. Concomitant Therapy

Any medication or vaccine (including over-the-counter or prescription medicines, vitamins, and/or herbal supplements) that the participant is receiving at the time of enrolment or receives during the study must be recorded along with:

- reason for use
- dates of administration including start and end dates
- dosage information including dose and frequency

The Medical Monitor should be contacted if there are any questions regarding concomitant or prior therapy.

Participants must abstain from taking prescription or non-prescription drugs (including dietary or herbal supplements but excluding simple analgesics and vitamins) within 7 days before the start of study treatment until completion of the follow-up visit, unless, in the opinion of the investigator and sponsor, the medication will not interfere with the study.

Paracetamol/Acetaminophen, at doses of ≤ 2 grams/day, is permitted for use any time during the study. Other concomitant medication may be considered on a case-by-case basis by the investigator in consultation with the Medical Monitor if required.

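### The 7-day limit on ordinary prior medicines takes no account of half-life, so a longer-acting medicine may still be partly present during the 120 h PK profile; a half-life term would be a cheap improvement

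*Protocol*

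**What the plan says.** Protocol Section 6.2, exclusion 8, excludes "Past or intended use of over-the-counter or prescription medication including herbal medications within 7 days prior to dosing" and adds that "Specific medications listed in Section 7.7 may be allowed". Section 7.7 sets the matching abstinence period, "within 7 days before the start of study treatment until completion of the follow-up visit". It leaves out simple analgesics and vitamins, permits paracetamol up to a stated daily amount, and allows a medicine that the investigator and sponsor judge will not interfere with the study. Other medication may be considered case by case.

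Some products have their own look-back in Section 6.2: live vaccines (exclusion 9, one month before screening), new chemical entities (exclusion 11, twelve months) and treatments in other studies (exclusion 12, "Current enrollment or past participation within the last 90 days before signing of consent in any other clinical study"). Exclusion 2 concerns disorders that alter absorption, metabolism or elimination, not medicines.

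On recording, Section 7.7 says that medication "that the participant is receiving at the time of enrolment or receives during the study must be recorded along with" its reason, dates and dosage. The Schedule of Activities starts the concomitant medication review on Day 1.

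PK is the primary endpoint, in two parallel arms of six sampled to 120 h after dosing. SAP Section 7.1.3.2 plans no statistical analysis of PK parameters. SAP Section 4 admits to the PK population every dosed participant with an analysed sample.

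**The concern.** A fixed number of days clears short-acting medicines and leaves long-acting ones partly on board. Someone who stopped a long-acting medicine just over seven days before dosing meets exclusion 8, and the interference judgement in Section 7.7 is not triggered because the medicine lies outside the window. No other criterion covers such a medicine, and the protocol does not permit waivers, so the wording of the criterion decides eligibility.

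If the residual medicine changed GSK2269557 exposure, that participant's profile would enter a descriptive summary of six. In a parallel design nobody serves as their own control, and the SAP has no rule or sensitivity analysis for prior medication. A medicine stopped before enrolment need not be recorded under Section 7.7, so the listings might not show a possible cause. At stake are the arm's geometric mean and the width of its interval.

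**Working it through.** **Inputs.** Window: 7 days = 168 h (Protocol 6.2, 7.7). Last PK sample: 120 h (5.4). Six per arm; between-participant SD on the log scale 0.346 for Cmax and 0.382 for AUC(0-24) (10.1). Exposure factor F for one affected participant: assumed, because the documents give none.

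**1. Reproduce the plan's precision.** Half-width of the 90% interval = t(0.95, 5 df) × SD / √6, with t = 2.015.
- Cmax: 2.015 × 0.346 / 2.449 = 0.285
- AUC(0-24): 2.015 × 0.382 / 2.449 = 0.314

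Both match Section 10.1. Raising the SD by 10% and 20% gives 0.313 and 0.342 for Cmax, and 0.346 and 0.377 for AUC(0-24), as in Section 10.1.1.

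**2. What seven days covers.** 168 / 5 = 33.6 h is the longest half-life for which five half-lives fit. With first-order elimination, the fraction left is 0.5^(168/h) at dosing and 0.5^(288/h) at the last sample, where h is the half-life in hours:

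| Half-life of prior medicine | Left at dosing | Left at 120 h |
|---|---|---|
| 24 h | 0.8% | 0.02% |
| 33.6 h | 3.1% | 0.3% |
| 72 h | 19.8% | 6.3% |
| 168 h | 50% | 30% |

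The half-lives are illustrative and do not stand for named medicines.

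**3. One affected participant in an arm of six.** The geometric mean is multiplied by F^(1/6). The expected SD becomes √(SD² + (ln F)²/6), and the half-width follows as in step 1.

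| F (assumed) | Mean multiplied by | Shift, log units | Cmax half-width | AUC(0-24) SD | AUC(0-24) half-width |
|---|---|---|---|---|---|
| none | 1 | 0 | 0.285 | 0.382 | 0.314 |
| 1.5 | 1.07 | 0.068 | 0.316 | 0.416 | 0.342 |
| 2 | 1.12 | 0.116 | 0.368 | 0.475 | 0.391 |
| 3 | 1.20 | 0.183 | 0.466 | 0.589 | 0.485 |

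A reduction by the same factor shifts the log mean equally in the other direction and widens the interval equally.

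**4. Comparison with the plan.** Every shift in the table is smaller than the planned half-widths of 0.285 and 0.314. Even F = 5 gives ln 5 / 6 = 0.268. Precision is more sensitive: at F = 2 both half-widths exceed the protocol's own +20% case (0.368 against 0.342, and 0.391 against 0.377). At F = 1.5 they lie close to the +10% case.

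Steps 2 and 3 are not linked. Nothing in the documents turns a residual fraction into a value of F.

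**The case against.** The strongest reply is that the premise is missing. Neither document gives the metabolic pathway of GSK2269557 or a measured interaction. Whether seven days is enough depends on the Investigator's Brochure, which is not available here. The dietary rule ("Refrain from consumption of Seville oranges, grapefruit or grapefruit juice from 7 days before the start of study treatment") gives no mechanism and uses the same seven days, so Sections 6.2, 6.3.1 and 7.7 do not contradict each other. This stands, and it makes the consequence conditional.

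Three stronger readings are tempting but unsupported.
- A reader might infer that one flat limit governs every prior medicine. It does not: vaccines, new chemical entities and other-study treatments have separate windows, and Section 7.7 exempts some medicines.
- A reader might take the contraception period in Section 6.1 ("for at least 5 half-lives + 90 days after the last dose of study treatment") as a precedent. It concerns the study drug, not prior medicines.
- A reader might infer that an interacting medicine will distort an arm. No interaction is shown, and no likelihood can be given that one of twelve volunteers would be affected.

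It is also fair to say that participants must be overtly healthy on medical history, and that the screening history covers drug use. Individual profiles are plotted and listed, and the SAP requires exclusions from summaries to be documented with reasons. These measures narrow the gap and could make an odd profile visible. They do not close it: none sets a limit on a recently stopped medicine, and a visible outlier cannot be explained if the medicine was never recorded.

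**Conclusion.** The point holds in a limited form. For ordinary over-the-counter, prescription and herbal medicines, the eligibility window ignores half-life, and seven days gives five half-lives only up to 33.6 h. Beyond that, some of the medicine may remain during the PK profile.

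The size rests on two assumptions: that one of six participants is affected, and that exposure changes 1.5- to 3-fold. On those assumptions the arm geometric mean moves 7% to 20%, inside the planned 90% half-width, and the AUC(0-24) half-width rises from 0.314 to about 0.34 to 0.49. The study is descriptive and sized on feasibility, so no test or error rate is affected. This is a cheap improvement to the eligibility wording, not a demonstrated threat to the primary endpoint.

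**What to change.** In exclusion 8, and in the matching sentence of Section 7.7, add after the seven days: *or 5 half-lives of the medicine, whichever is longer*. Keep the Section 7.7 allowances, including the one for medicines that the investigator and sponsor judge will not interfere, and make clear that they apply to exclusion 8 as well. Extend the recording requirement to medicines stopped within that window, so that they appear in the SAP's medication listing (Listing 10).

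This is an eligibility limit only and asks nobody to stop a treatment.

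The cost is a half-life check at screening and possibly a few more screen failures; the non-interference allowance should keep these few. One overlap needs care: Appendix 2 accepts injectable and implanted hormonal contraception and foresees continued HRT, but Section 7.7 names none of these. The sponsor should state how they fit with the reworded limit.

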6.3. Lifestyle Restrictions

6.3.1. Meals and Dietary Restrictions

- Refrain from consumption of Seville oranges, grapefruit or grapefruit juice from 7 days before the start of study treatment until collection of the final pharmacokinetic (PK) sample.

6.3.2. Caffeine, Alcohol, and Tobacco

- Participants will abstain from ingesting caffeine- or xanthine-containing products (eg, coffee and cola drinks) for 6 hours before the start of dosing until after collection of the final pharmacokinetic (PK) and/or pharmacodynamic sample.
- Participants will abstain from alcohol for 12 hours before the start of dosing until after collection of the final PK and/or pharmacodynamic sample.
- Smoking is not permitted during the study.

6.3.3. Activity

- Participants will abstain from strenuous exercise for a minimum of 48 hours before each blood collection for clinical laboratory tests. Participants may participate in light recreational activities during studies (eg, watching television, reading).

6.4. Screen Failures

Screen failures are defined as participants who consent to participate in the clinical study but are not subsequently randomized. A minimal set of screen failure information is required to ensure transparent reporting of screen failure participants to meet the Consolidated Standards of Reporting Trials (CONSORT) publishing requirements and to respond to queries from regulatory authorities. Minimal information includes

demography, screen failure details, eligibility criteria, and any serious adverse events (SAEs).

Individuals who do not meet the criteria for participation in this study (screen failure) may be rescreened. Rescreened participants should be assigned a new participant number.

7. TREATMENTS

Study treatment is defined as any investigational treatment(s), marketed product(s), placebo, or medical device(s) intended to be administered to a study participant according to the study protocol.

7.1. Treatments Administered

Study Treatment Name:	GSK2269557 ELLIPTA™ DPI (500 µg)	GSK2269557 ELLIPTA™ DPI (750 µg)
Dosage formulation:	DPI	DPI
Unit dose strength(s)/Dosage level(s):	500 µg	750 µg
Route of Administration	Inhalation	Inhalation
Dosing instructions:	Inhale as directed	Inhale as directed
Packaging and Labelling	Study Treatment will be labelled as required per country requirement.	Study Treatment will be labelled as required per country requirement.
Manufacturer	GSK	GSK
Device:	ELLIPTA™	ELLIPTA™

7.2. Dose Modification

This protocol does not allow alteration from the currently outlined dosing schedule.

7.3. Method of Treatment Assignment

Study using Pre-Coded Randomization	On Day 1, participants will be assigned a unique number (randomization number) in ascending numerical order by the Interactive Voice Recognition System/ Web Response Centre (IVRS/IWRS). The randomization number encodes the participant's assignment to one of the treatment arms of the study, according to the randomization schedule generated prior to the study by the Clinical Statistics Department at GSK. Each participant will be dispensed blinded study treatment, labelled with a unique container number.
-------------------------------------	--

7.4. Blinding

Blind Break (IVRS/IWRS)	The IVRS/IWRS will be programmed with blind-breaking instructions. The blind may be broken by the investigator or treating physician in the case of an emergency, or if, in the opinion of the investigator, it is in the participant's best interest for the investigator to know the study treatment assignment. The investigator is encouraged to discuss with the GSK Medical Monitor or appropriate GSK study personnel before the blind is broken. If GSK is not notified before the blind is broken, they must be notified as soon as possible after breaking the blind. The date and reason that the blind was broken must be recorded in the source documentation and CRF, as applicable.
-------------------------	--

A participant may continue in the study if that participant's treatment assignment is unblinded. The primary reason for discontinuation (the event or condition which led to the unblinding) will be recorded in the case report form (CRF).

GlaxoSmithKline's (GSK) Global Clinical Safety and Pharmacovigilance (GCSP) staff may unblind the treatment assignment for any participant with an SAE. If the SAE requires that an expedited regulatory report be sent to one or more regulatory agencies, a copy of the report, identifying the participant's treatment assignment, may be sent to investigators in accordance with local regulations and/or GSK policy.

7.5. Preparation/Handling/Storage/Accountability

1. The investigator or designee must confirm appropriate temperature conditions have been maintained during transit for all study treatment received and any discrepancies are reported and resolved before use of the study treatment.
2. Only participants enrolled in the study may receive study treatment and only authorized site staff may supply or administer study treatment. All study treatments must be stored in a secure, environmentally controlled, and monitored (manual or automated) area in accordance with the labeled storage conditions with access limited to the investigator and authorized site staff.

3. The investigator, institution, or the head of the medical institution (where applicable) is responsible for study treatment accountability, reconciliation, and record maintenance (ie, receipt, reconciliation, and final disposition records).
4. Further guidance and information for the final disposition of unused study treatment are provided in the Study Reference Manual.
 - Under normal conditions of handling and administration, study treatment is not expected to pose significant safety risks to site staff.
 - A Material Safety Data Sheet (MSDS)/equivalent document describing occupational hazards and recommended handling precautions either will be provided to the investigator, where this is required by local laws, or is available upon request from GSK.

7.6. Treatment Compliance

- When participants are dosed at the site, they will receive study treatment directly from the investigator or designee, under medical supervision. The date and time of each dose administered in the clinic will be recorded in the source documents. The dose of study treatment and study participant identification will be confirmed at the time of dosing by a member of the study site staff other than the person administering the study treatment.

7.7. Concomitant Therapy

Any medication or vaccine (including over-the-counter or prescription medicines, vitamins, and/or herbal supplements) that the participant is receiving at the time of enrolment or receives during the study must be recorded along with:

- reason for use
- dates of administration including start and end dates
- dosage information including dose and frequency

The Medical Monitor should be contacted if there are any questions regarding concomitant or prior therapy.

Participants must abstain from taking prescription or non-prescription drugs (including dietary or herbal supplements but excluding simple analgesics and vitamins) within 7 days before the start of study treatment until completion of the follow-up visit, unless, in the opinion of the investigator and sponsor, the medication will not interfere with the study.

Paracetamol/Acetaminophen, at doses of ≤ 2 grams/day, is permitted for use any time during the study. Other concomitant medication may be considered on a case-by-case basis by the investigator in consultation with the Medical Monitor if required.

